### 3.10.1 Off Study Procedure

Authorized staff must notify Central Registration Office (CRO) when a patient is taken off-study. An off-study form from the web site

<http://intranet.cancer.gov/ccr/welcome.htm> must be completed and faxed to [contact].

### 3.11 Follow-Up for Progression Free Survival and Duration of Response

An objective of this study is to determine progression free survival and duration of response in patients who achieve either a Complete Response (CR) or a Partial Response (PR). Patients who achieve either a CR or PR and stop receiving study drug will be monitored periodically to follow the course of their response. This follow-up period will vary per patient, but in general will consist of a CT scan every 6 weeks, extending to every 3 to 4 months, per PI discretion. This follow-up may be done here at the NIH Clinical Center, or via the patient's local physician, with scans sent in for inclusion in our trial results. Physical exams, including pelvic exams, will also be done at the same time points.

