#### Secondary-

- Assess pharmacodynamic endpoints to determine the extent of tubulin polymerization and whether or not there has been activation of cellular death pathways “distal” to the target.
- Estimate progression free survival and duration of response.

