#### 1.1.2 Secondary:

- Assess pharmacodynamic endpoints after ixabepilone administration to determine the extent of tubulin polymerization and whether or not there has been activation of cellular death pathways “distal” to the target.
- Determine progression free survival and duration of response

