### 3.10 OFF-STUDY CRITERIA

This study does not involve a preset period of monitoring or follow-up after a patient has reached off treatment status. In most cases the Off-treatment and Off-Study dates will be the same. If a patient has a treatment related toxicity, and in the opinion of the PI it is prudent and medically necessary to monitor the patient further, an individual patient may remain on-study, but off-treatment until such time the PI determines it safe to remove them from study.

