### 5.4 STATISTICAL SECTION

#### STUDY OBJECTIVES:

Primary: To establish the activity of ixabepilone administered daily as a one-hour infusion on five successive days (daily x 5), every three weeks in patients with cervical carcinoma previously treated with chemotherapy, as determined by overall response (PR+CR). Activity will be measured using standard RECIST guidelines.

Secondary: Assess pharmacodynamic endpoints after ixabepilone administration to determine the extent of tubulin polymerization and whether or not there has been activation of cellular death pathways “distal” to the target, and to estimate the progression free survival and duration of response.

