As secondary endpoints, progression free survival and duration of response will also be evaluated, using Kaplan-Meier curves. Progression free survival will be measured from the on-study date until the date of progression or last follow-up if the patient has not progressed. Response duration will be determined beginning at the date a PR or CR is first noted and will last until the patient is noted to have progressive disease relative to the response identified.

Women, 18 years of age or older, from all racial and ethnic backgrounds, will be eligible for the study.

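### The PFS definition does not count death as an event, and post-treatment progression scans are scheduled only for responders although PFS is stated as an objective without restriction

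*Combined protocol and SAP*

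**What the plan says.** The PFS objective appears three times without restriction to responders: in the Précis ("Estimate progression free survival and duration of response"), in 1.1.2 ("Determine progression free survival and duration of response") and in the objectives at the head of 5.4 ("to estimate the progression free survival and duration of response"). Section 5.4.1 plans Kaplan-Meier curves and gives the rule: "Progression free survival will be measured from the on-study date until the date of progression or last follow-up if the patient has not progressed". Death is not mentioned.

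Section 3.11, whose title covers both PFS and duration of response, opens more narrowly: "An objective of this study is to determine progression free survival and duration of response in patients who achieve either a Complete Response (CR" and continues with partial response. It then provides: "Patients who achieve either a CR or PR and stop receiving study drug will be monitored periodically to follow the course of their response". The interval is generally six-weekly CT, lengthening to three to four months at the PI's discretion, and scans may be done locally.

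For everyone else, 3.10 says "This study does not involve a preset period of monitoring or follow-up after a patient has reached off treatment status" and "In most cases the Off-treatment and Off-Study dates will be the same". The only extension it states is for treatment-related toxicity, at the PI's judgement.

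**The concern.** There are two separate defects.

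**Event definition.** A patient who dies before progression is documented has not progressed, so the 5.4.1 rule sends her to censoring. She is then treated as if her later risk matched that of patients still alive and progression-free. The protocol's own account of a randomized ixabepilone trial (1.2.4) uses a PFS that includes death, so results under the two definitions would not be comparable.

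**Follow-up that depends on response.** Section 3.9 lets patients leave treatment without progression, for example for toxicity, withdrawal or PI discretion. If two patients stop for toxicity, one in partial response and one with stable disease, 3.11 schedules scans for the first and nothing schedules them for the second. The second is censored at or near the stop. Censoring is then tied to outcome, and a confidence interval would not show it. Patients who stop because of progression already have their event and are not affected.

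What is at stake is the PFS curve and any comparison of it with the PFS figures quoted in 1.2.4. The activity decision is not at stake.

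**Working it through.** **1. The plan's own figures.** The plan states no sample size, event count or power for PFS. Its only design figures concern response (0/12, then at least 4/37). Early termination at 5% is 0.95^12 = 0.540, against a stated 0.54. The exact probability of declaring activity is 0.0935 at 5% and 0.9024 at 20%, within the stated alpha and beta of 0.10. Enrollment is 2 × 37 + 2 = 76. None of these uses PFS.

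**2. Deaths censored.** Suppose the death is censored at its own date. The risk sets are unchanged, and a factor of at most 1 drops out of the Kaplan-Meier product, so the curve is never lower. (If it is censored at an earlier visit, the risk sets in between also shrink, and this ordering is no longer guaranteed at every time point.) Let d be the share of PFS events that are deaths without documented progression; d is assumed. Under a constant hazard the median is multiplied by 1/(1 − d):

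- d = 5%: 1/0.95 = 1.053
- d = 10%: 1/0.90 = 1.111
- d = 20%: 1/0.80 = 1.250

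**3. Follow-up gap.** The assumed inputs are q, the share who stop without progression, and k, their later hazard relative to the hazard on treatment. Take the reported median as the time unit, so h = ln 2. The stopping hazard is mu = h·q/(1 − q). Kaplan-Meier with censoring at the stop estimates exp(−ht). With everyone followed, the true curve is

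S(t) = exp(−(h+mu)t) + mu·[exp(−kht) − exp(−(h+mu)t)]/(h + mu − kh).

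Example, q = 20% and k = 2: mu = 0.693 × 0.25 = 0.173. S(t) = 0.5 at t = 0.940, so the reported median is 1/0.940 − 1 = 6.4% too long. Error in the reported median:

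| k | q = 10% | q = 20% | q = 30% |
|---|---|---|---|
| 0.5 | −2.2% | −4.8% | −8.1% |
| 1 | 0 | 0 | 0 |
| 1.5 | +1.7% | +3.6% | +5.9% |
| 2 | +3.0% | +6.4% | +10.4% |
| 3 | +4.9% | +10.5% | +17.0% |

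A simulation in which 5–20% of patients are responders (hazard 0.4h) and are never censored gave −1.5% to −7.4% at k = 0.5, +0.1% to +2.6% at k = 1, and +3.1% to +17.2% at k = 2–3.

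**4. A different set of assumptions.** A second simulation used median PFS of 2.5 months in non-responders and 7 in responders, with 10–20% responding. Among non-responders, 10–30% stopped at a uniformly distributed fraction of their time to event, and 5–20% had death without progression as the first event. Both defects together lengthened the median by about 12% (3.31 against 2.96 months) to 53% (4.15 against 2.72). With deaths counted, the follow-up gap alone gave about 7% (2.91 against 2.72) to 25% (3.42 against 2.73). The answer is thus driven by what is assumed about who stops and when.

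**5. Scale.** The relative standard error of an exponential median is 1/(ln 2·√n), ignoring censoring: 0.237 at n = 37 and 0.416 at n = 12. With 30% censored, a simulation put it at about 27% and 56%.

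**6. Bound from a sensitivity analysis.** Counting every stop without progression as an event gives a median of h/(h + mu) = 1 − q times the reported one: 0.90, 0.80 or 0.70.

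**The case against.** PFS carries no hypothesis, threshold or decision here, and several provisions narrow the gap. Section 3.9.1 and column F of Appendix B give imaging at the end of treatment or study, so progression present then becomes an event. Section 5.2 asks for efforts to document progression after symptomatic deterioration, which covers some of the patients most likely to have k well above 1. Section 5.1 admits outside radiology reports. Section 7.3.4 requires every on-study death to be reported whatever its cause, and 7.2.1 sends deaths not due to progressive disease to the IRB. Section 5.2 also groups early deaths with failures and labels that group as disease progression, and 1.2.4 suggests the authors understand PFS to include death.

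Much of this stands. It shows that the death problem is mainly one of wording rather than missing data, and that the follow-up gap falls mainly on non-responders who stop for toxicity or at the PI's discretion. It does not remove either defect. The end-of-treatment imaging is a single assessment; the symptomatic-deterioration text has no schedule; toxicity follow-up is not tumor follow-up. The 5.2 failure rule governs the response analysis and includes patients of unknown status, who could not sensibly be PFS events; 5.4.1 does not adopt it.

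It could also be said that 3.11 meant PFS for responders only. That conflicts with the Précis, 1.1.2, 5.4 and 5.4.1, and would condition PFS on a later outcome.

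**Conclusion.** Wrong as written, for a secondary endpoint; it should be corrected. The firm part is the death omission: a literal reading of 5.4.1 lengthens the median by about 5%, 11% or 25% for d = 5%, 10% or 20%, with d assumed, a constant hazard, and censoring at the date of death. Only at about d = 20% does this reach the standard error for a full cohort of 37.

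The follow-up defect is also textual: 3.11 conflicts with the unrestricted objective, and post-treatment ascertainment depends on response. A reader might infer that this inflates PFS by a known amount. The documents do not support that. They give neither q nor k; the error runs from −8.1% to +17.0% over the range in step 3, is zero at k = 1, and stays below the standard error at both n = 37 and n = 12. Under the informative stopping times of step 4 it is always upward and at most about equal to the n = 37 standard error, but nothing in the documents favors that model.

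A reader might also infer that on-study deaths go unrecorded, or that the activity conclusion is compromised. Neither follows: on-study deaths are reported under section 7, and the response endpoint and the two-stage rule do not use PFS.

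**What to change.** 1. In 5.4.1, define PFS for all enrolled patients as the time from the on-study date to progression or death from any cause, censored at the last adequate tumor assessment. State how new anticancer therapy before progression is handled.
2. Align 3.10 and 3.11 so that every consenting patient off treatment without progression has the assessment intervals that 3.11 gives responders, using the local-physician scans it already allows. Collecting dates alone would leave detection of progression dependent on response. If the common schedule is not feasible, collect progression and death dates from records and report the differential ascertainment as a limitation.
3. Add a sensitivity analysis that counts going off treatment without progression as an event.
4. Reconcile 3.3.1 and 3.3.3, which speak of removal from the study for certain toxicities, with 3.9, which speaks of going off treatment, so that it is clear whether follow-up continues.

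The cost is protocol wording plus modest record and scan collection, for about 4 to 11 patients per full cohort at the assumed 10–30% (37 × 0.10 = 3.7; 37 × 0.30 = 11.1). Section 6.3.3 already asks patients to have a local physician. Patients who withdraw consent stay censored, and reported PFS may be shorter. Sample size does not change.

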## 4 SUPPORTIVE CARE

1. Febrile neutropenia is a life-threatening complication requiring hospitalization and urgent broad-spectrum antibiotics. Growth factors may be used in accordance with the ASCO guidelines. Growth factors should not be used to raise neutrophil counts in order to begin chemotherapy on time. Such cases will be evaluated individually to determine the toxicity grade.
2. Symptomatic anemia should be treated with appropriate red blood cell support and transfusion is recommended if the hemoglobin falls below 8 g/dl. Alternately recombinant erythropoietin may be used if desired by the patient's local physician.
3. Thrombocytopenia should be treated conservatively. In the absence of bleeding or a planned invasive procedure, platelet transfusions should only be given for a platelet count below 10,000. If invasive procedures are planned or the patient develops bleeding, platelet transfusions should be administered in accordance with standard of practice, usually maintaining a platelet count  $\geq 50,000/\text{mm}^3$ .
4. Central venous access devices such as a temporary internal jugular line, PICC lines via the brachial vein, semi-permanent HICKMAN®, GROSHONG®, or medi-port implanted devices are acceptable for this study. All devices will have nursing supervision to include patient self care and cleaning/flushing of the devices.
5. Nutritional assessment and psychological support: Refractory neoplasms are commonly complicated by malnutrition. Patients with weight loss or evidence of wasting syndrome should have a nutritional consult. Patients who are having emotional difficulties dealing with their treatment, and disease, or those patients who request assistance, will be referred to a Social Worker for evaluation and support.
6. Care of the fingernails during ixabepilone trial participation is encouraged. A patient information form is included in APPENDIX D.

## 5 DATA COLLECTION and EVALUATION

### 5.1 DATA COLLECTION AND RECORD KEEPING

Data will be prospectively collected and entered into the database at least once every two weeks. The NCI C3D database will be used for this report. The responsible investigator is [name]. All radiographic images will be stored in the Department of Radiology, Clinical Center, NIH. All radiographic images will be reviewed by a staff radiologist for validity and reliability. The original signed consent goes to Medical Records; copy placed in research record

All patients must have signed an informed consent and an on study confirmation of confirmation of eligibility form must be filled out before enrollment.

Complete records must be maintained on each patient. These will consist of the hospital chart with any supplementary information obtained from outside laboratories, radiology reports, or physician's records. These records will serve as the primary source material that forms the basis for the research record. All relevant data will also be entered into the NCI C3D database from which formal analyses are done. The primary source documentation will assure the following: on study information, including patient eligibility data and patient history; and off-study summary sheets, including a final assessment by the treating physician.

Data will be submitted to the CTEP/CDUS every three months via the NCI C3D database.

### 5.2 RESPONSE CRITERIA (RECIST)

#### Eligibility:

Only patients with measurable disease at baseline can have objective tumor response evaluated as an endpoint.

Measurable disease: The presence of at least one measurable lesion. If the measurable disease is restricted to a solitary lesion, its neoplastic nature should be confirmed by cytology/histology, if possible.

Measurable lesions: Lesions that can be accurately measured in at least one dimension with longest diameter  $\geq 20$  mm using conventional techniques or  $\geq 10$  mm with spiral CT scan.

Non-measurable lesions: All other lesions, including small lesions (longest diameter  $< 20$  mm with conventional techniques or  $< 10$  mm with spiral CT scan), bone lesions, leptomeningeal disease, ascites, pleural/pericardial effusion, inflammatory breast disease, lymphangitis cutis/pulmonis, cystic lesions, and also abdominal masses that are not confirmed and followed by imaging techniques.

- All measurements should be taken and recorded in metric notation, using a ruler or calipers. All baseline evaluations should be performed as closely as possible to the beginning of treatment and never more than 4 weeks before the beginning of the treatment.
- The same method of assessment and the same technique should be used to characterize each identified and reported lesion at baseline and during follow-up.

- Clinical lesions will only be considered measurable when they are superficial (e.g., skin nodules and palpable lymph nodes). For the case of skin lesions, documentation by color photography, including a ruler to estimate the size of the lesion, is recommended.

Methods of Measurement:

- CT and MRI are the best currently available and reproducible methods to measure target lesions selected for response assessment. Conventional CT and MRI should be performed with cuts of 10 mm or less in slice thickness contiguously. Spiral CT should be performed using a 5 mm contiguous reconstruction algorithm. This applies to tumors of the chest, abdomen and pelvis. Head and neck tumors and those of extremities usually require specific protocols.
- Lesions on chest X-ray are acceptable as measurable lesions when they are clearly defined and surrounded by aerated lung. However, CT is preferable.
- For accurate objective response evaluation, ultrasound (US) should not be used to measure tumor lesions. However, US is a possible alternative to clinical measurements of superficial palpable lymph nodes, subcutaneous lesions and thyroid nodules. US might also be useful to confirm the complete disappearance of superficial lesions usually assessed by clinical examination.
- The utilization of endoscopy and laparoscopy for objective tumor evaluation has not yet been fully and widely validated. Their uses in this specific context require sophisticated equipment and a high level of expertise. Therefore, the utilization of such techniques for objective tumor response should be restricted to validation purposes. However, such techniques can be useful in confirming complete pathological response when biopsies are obtained.

Baseline documentation of "Target" and "Non-Target" lesions:

- All measurable lesions up to a maximum of five lesions per organ and 10 lesions in total, representative of all involved organs should be identified as target lesions and recorded and measured at baseline.
- Target lesions should be selected on the basis of their size (lesions with the longest diameter) and their suitability for accurate repeated measurements (either by imaging techniques or clinically).
- A sum of the longest diameter (LD) for all target lesions will be calculated and reported as the baseline sum LD. The baseline sum LD will be used as reference by which to characterize the objective tumor.
- All other lesions (or sites of disease) should be identified as non-target lesions and should also be recorded at baseline. Measurements of these lesions are not required, but the presence or absence of each should be noted throughout follow-up.

Response Criteria:

Evaluation of target lesions:

- Complete Response (CR): Disappearance of all target lesions.
- Partial Response (PR): At least a 30% decrease in the sum of the LD of target lesions, taking as reference the baseline sum LD.
- Progressive Disease (PD): At least a 20% increase in the sum of the LD of target lesions, taking as reference the smallest sum LD recorded

since the treatment started or the appearance of one or more new lesions.

Stable Disease (SD): Neither sufficient shrinkage to qualify for PR nor sufficient increase to qualify for PD, taking as reference the smallest sum LD since the treatment started.

Evaluation of non-target lesions:

Complete Response (CR): Disappearance of all non-target lesions and normalization of tumor marker level.

Incomplete Response/  
Stable Disease (SD): Persistence of one or more non-target lesion(s) and/or maintenance of tumor marker level above the normal limits.

Progressive Disease (PD): Appearance of one or more new lesions and/or unequivocal progression of existing non-target lesions [Although a clear progression of "non target" lesions only is exceptional, in such circumstances, the opinion of the treating physician should prevail and the progression status should be confirmed later on by the review panel (or study chair)].

Evaluation of best overall response:

The best overall response is the best response recorded from the start of the treatment until disease progression/recurrence (taking as reference for PD the smallest measurements recorded since the treatment started). In general, the patient's best response assignment will depend on the achievement of both measurement and confirmation criteria.

Target Lesion	Non-Target Lesion	New Lesions	Overall Response
CR	CR	No	CR
CR	Incomplete Response/SD	No	PR
PR	Non-PD	No	PR
SD	Non-PD	No	SD
PD	Any	Yes or No	PD
Any	PD	Yes or No	PD
Any	Any	Yes	PD

- Patients with a global deterioration of health status requiring discontinuation of treatment without objective evidence of disease progression at that time should be classified as having "symptomatic deterioration". Every effort should be made to document the objective progression even after discontinuation of treatment.
- In some circumstances it may be difficult to distinguish residual disease from normal tissue. When the evaluation of complete response depends on this determination, it is recommended that the residual lesion be investigated (fine needle aspirate/biopsy) to confirm the complete response status.

Confirmation:

- The main goal of confirmation of objective response is to avoid overestimating responses. In cases where confirmation of response is not feasible, it should be made clear when reporting the outcome that the response(s) is(are) not confirmed.
- To be assigned a status of PR or CR, changes in tumor measurements must be confirmed by repeat assessments that should be performed no less than 4 weeks after the criteria for response are first met. Longer intervals as determined by the study protocol may also be appropriate.
- In the case of SD, follow-up measurements must have met the SD criteria at least once after study entry at a minimum interval, not less than 6 weeks.

Duration of overall response:

- The duration of overall response is measured from the time measurement criteria are met for CR or PR (whichever status is recorded first) until the first date that recurrence or PD is objectively documented, taking as reference for PD the smallest measurements recorded since the treatment started.

Duration of stable disease:

- SD is measured from the start of the treatment until the criteria for disease progression are met, taking as reference the smallest measurements recorded since the treatment started.

Response review:

- Responses will be reviewed by an expert(s) independent of the study at the study's completion. Simultaneous review of the patients' files and radiological images will be conducted.

Reporting of results:

- All patients initially considered evaluable will be assessed for response to treatment, even if there are major protocol treatment deviations or if they are ineligible. Each patient will be assigned one of the following categories: 1) complete response, 2) partial response, 3) stable disease, 4) progressive disease, 5) early death from malignant disease, 6) early death from toxicity, 7) early death because of other cause, or 8) unknown (not assessable, insufficient data).
- All of the patients who met the eligibility criteria and are evaluable, will be included in the main analysis of responses. Patients in response categories 4-8 will be considered as failing to respond to treatment (disease progression). Thus, an incorrect treatment schedule or drug administration will not result in exclusion from the analysis of a response.
- All conclusions will be based on all eligible patients.
- Sub-analyses may be performed on the basis of a subset of patients, excluding those for whom major protocol deviations have been identified (e.g., early death due to other reasons, early discontinuation of treatment, major protocol violations, etc.). However, these sub-analyses may not serve as the basis for

drawing conclusions concerning treatment efficacy, and the reasons for excluding patients from the analysis will be clearly reported.

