In the single arm trial of ixabepilone monotherapy patients with measurable disease who had tumor progression while receiving prior anthracycline, taxane, and capecitabine were enrolled. Ixabepilone 40 mg/m^2 monotherapy was administered as a 3-hour intravenous infusion on day 1 of a 21-day cycle. The primary end point was objective response rate (ORR), assessed by an independent radiology facility (IRF). A total of 126 patients were treated and 113 were assessable for response. Patients were heavily pretreated with 88% having received at least two lines of prior chemotherapy in

the metastatic setting. IRF-assessed ORR was 11.5% (95% CI, 6.3% to 18.9%) for response-assessable patients. Investigator-assessed ORR for all treated patients was 18.3% (95% CI, 11.9% to 26.1%). Fifty percent of patients achieved stable disease (SD); 14.3% achieved SD  $\geq$  6 months. Median duration of response and progression-free survival were 5.7 and 3.1 months, respectively. Median overall survival was 8.6 months. Patients received a median of 4.0 treatment cycles (range, one to 16 cycles), and 25% of patients received  $\geq$  eight cycles. Grade 3/4 treatment-related events included peripheral sensory neuropathy (14%), fatigue/asthenia (13%), myalgia (8%), and stomatitis/mucositis (6%). Resolution of grade 3/4 peripheral sensory neuropathy occurred after a median period of 5.4 weeks. The authors concluded that ixabepilone demonstrated clear activity and a manageable safety profile in patients with MBC resistant to anthracycline, taxane, and capecitabine. Responses were durable and notable in patients who had not previously responded to multiple prior therapies.

Ixabepilone has also been evaluated in the neoadjuvant setting [58]. That study was designed to determine the pathological response obtained with ixabepilone as neoadjuvant therapy for breast cancer and to obtain tumor samples for analysis of gene expression and identification of potential predictors of response to ixabepilone. Based on the genomic study, patients with hormone receptor–negative disease were more likely to respond to ixabepilone [58].

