#### 5.4.1 Trial Design:

This trial of Ixabepilone in patients with cervical carcinoma will be conducted using a two-stage optimal design (Simon, R, Controlled Clinical Trials, 10:1-10, 1989). With  $\alpha = 0.10$  (the probability of incorrectly accepting a poor agent), and  $\beta = 0.10$  (the probability of incorrectly rejecting a good agent), we will try to rule out an undesirably low overall response (PR+CR) probability of 5% ( $p_0 = 0.05$ ) in favor of a level indicative of modest activity, 20% ( $p_1 = 0.20$ ).

Several histologic subtypes of cervical carcinoma are recognized including: (1) squamous cell (2) adenocarcinoma (3) adenosquamous carcinoma and (4) other. Among these, squamous is the most common histologic diagnosis, with adenocarcinoma second in frequency. While chemotherapy has not been shown to be very effective in cervical carcinoma, differences among the histologic subtypes in response to therapy may exist. In order to properly evaluate the activity of ixabepilone in cervical cancer, we will stratify patients into two cohorts according to histologic subtypes: (1) squamous cell (2) non-squamous including adenocarcinoma, adenosquamous carcinoma and non-squamous-not otherwise specified.

Initially, 12 evaluable patients will be enrolled in each of the two cohorts. If 0/12 demonstrate an objective response (PR +CR), then accrual to that cohort will stop and the agent will be considered inactive in this population. If one or more patients have a response, accrual will continue until a total of 37 evaluable patients have been enrolled in that cohort. If 1 - 3 of 37 patients demonstrates a response in a cohort, this will be

considered insufficient activity, and the agent will not be considered worthy of further development in that cohort. If 4 or more of 37 patients in the entire cohort have a response, then the agent will be considered active in that group (and at least potentially able to produce a response level consistent with 20%). Under the null hypothesis ( $p_0 = 0.05$ ), the probability of early termination of accrual to any one group is 0.54. With two cohorts of patients, the maximum number of evaluable patients in the two cohorts would be 74. However, in the event that an inevaluable patient is enrolled in each cohort, a total enrollment ceiling of 76 patients will be requested. Our goal is to enroll adenocarcinoma patients, but we do not want to refuse squamous cell carcinoma patients who have no other therapeutic options.

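### Independent response review comes only at study completion, after the 0/12 decision it could protect; one patient wrongly counted as a responder opens stage 2, and the plan does not say whose reading governs

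*Combined protocol and SAP*

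**What the plan says.** - **Timing of independent review.** Section 5.2, under response review: "Responses will be reviewed by an expert(s) independent of the study at the study's completion". No section ties an independent review to the stage-1 look, and 5.2 does not say what follows if the expert disagrees with the local reading.
- **Stage-1 rule.** Section 5.4.1: "Initially, 12 evaluable patients will be enrolled in each of the two cohorts". Then: "If 0/12 demonstrate an objective response (PR +CR), then accrual to that cohort will stop". One or more responses take the cohort on to 37 evaluable patients, and 4 or more of 37 means the drug is called active. The section does not say whether the local or the independent reading is counted, at either step.
- **Other safeguards.** Section 5.1 has a staff radiologist review all images. It does not call that review independent or give its timing. Section 5.2 requires a repeat assessment at least 4 weeks later before PR or CR is assigned. It also lets responses be reported as unconfirmed, if so labelled, where confirmation is not feasible. Section 5.4.1 does not say whether such a response counts at stage 1.
- **Evidence that readings differ.** Section 1.2.4, on the single-arm breast cancer monotherapy trial, gives 11.5% by independent radiology among 113 assessable patients. For all 126 treated it says: "Investigator-assessed ORR for all treated patients was 18.3% (95% CI, 11.9% to 26.1"%).

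**The concern.** The plan already provides for an independent review, but places it after the only interim decision in each cohort. That decision turns on a single patient: 0/12 stops and 1/12 continues. If the later review removes the only stage-1 response, up to 25 further patients will have been enrolled in a cohort that should have closed.

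The stated early-termination probability of 0.54 assumes that counted responses are true ones. Because 5.4.1 names no governing reading, the primary endpoint can also be counted in two ways at the end, and the error rates of those two counts may differ.

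**Working it through.** **Inputs from 5.4.1.** Alpha 0.10 ("the probability of incorrectly accepting a poor agent"), beta 0.10 ("the probability of incorrectly rejecting a good agent"), p0 = 0.05, p1 = 0.20, n1 = 12, stop at 0, n = 37, active at 4 or more. Stage 2 adds 37 − 12 = 25 patients.

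**Step 1: reproduce the plan.**
- Early termination at p0: 0.95^12 = 0.540 (stated: 0.54).
- Type I error = Σ P(X1 = x) · P(X2 ≥ 4 − x) over x ≥ 1, with X1 ~ Bin(12, 0.05) and X2 ~ Bin(25, 0.05):
  - x = 1: 0.3413 × 0.1271 = 0.0434
  - x = 2: 0.0988 × 0.3576 = 0.0353
  - x = 3: 0.0173 × 0.7226 = 0.0125
  - x ≥ 4: 0.0022
  - Sum: 0.0935
- Power at p1: 0.902.
- Expected cohort size at p0: 12 + 25 × (1 − 0.540) = 23.5.

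The design is correctly specified for true responses.

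**Step 2: an assumed local-read rate.** The documents give no false-response rate for this trial, so I borrow the ratio from the trial in 1.2.4.
- As printed: 18.3/11.5 = 1.59. Local rate 0.05 × 1.59 = 0.0796.
- On a common denominator, with counts inferred from the percentages (23/126 and 13/126): 23/13 = 1.77. Local rate 0.0885.

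Writing the local rate as q = 0.05 + 0.95f, these correspond to per-patient false-response rates f among true non-responders of (0.0796 − 0.05)/0.95 = 3.1% and (0.0885 − 0.05)/0.95 = 4.0%.

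**Step 3: effect on stage 1.** Early termination is (1 − q)^12. Expected size is 12 + 25 × (1 − early termination). The chance that stage 2 opens when there are truly 0/12 responders is 1 − (1 − f)^12.

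| | No misreading | Ratio 1.59 | Ratio 1.77 |
|---|---|---|---|
| Early termination | 0.540 | 0.370 | 0.329 |
| Expected cohort size | 23.5 | 27.8 | 28.8 |
| Stage 2 opens, given true 0/12 | 0 | 0.32 | 0.39 |

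Over a wider assumed range, f = 1% gives early termination of 0.479 and expected size 25.0; f = 10% gives 0.153 and 33.2.

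**Step 4: allow for confirmation.** If a false response needs two independent over-reads at per-scan rate f, replace f by f². Early termination is then 0.95^12 × (1 − f²)^12: 0.534 at f = 3.1% and 0.530 at f = 4.0%, with expected size 23.6 and 23.8. The same reader, lesions and baseline make errors correlated, which would put the result between these figures and those in Step 3.

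**Step 5: type I error under each possible governing reading.**
- Independent review decides 4/37, local reads decide only stage 1: add 0.540 × P(stage 2 opens given true 0/12) × P(X2 ≥ 4) to 0.0935, with P(X2 ≥ 4) = 0.0341.
  - Ratio 1.59: 0.0935 + 0.540 × 0.316 × 0.0341 = 0.099.
  - Ratio 1.77: 0.0935 + 0.540 × 0.391 × 0.0341 = 0.101.
  - Ceiling, with no stage-1 stop at all: P(≥ 4 of 37 at 5%) = 0.112.
- Local reads decide both rules: the Step 1 sum with q in place of 0.05 gives 0.29 and 0.36.

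**The case against.** The strongest reply is that the plan has more protection than the review sentence alone suggests.

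- A reader might infer that stage 1 rests on unreviewed reads. It does not: 5.1 has a staff radiologist review every image. What is missing is independence, and any stated link to stage 1.
- A reader might infer that one over-read scan opens stage 2. Section 5.2 requires confirmation at least 4 weeks later, and the natural reading is that 5.4.1 counts PR and CR so defined. One scan is then not enough unless unconfirmed responses are counted, which 5.4.1 neither allows nor excludes. With independent errors, confirmation removes nearly all of the effect (Step 4).
- The borrowed ratio comes from another tumour, its two rates have different denominators, and 1.2.4 does not describe how local reads were done there. It illustrates that readings can differ and does not estimate misreading in this trial.
- The added accrual is modest on average: about 4 to 5 patients per inactive cohort (27.8 − 23.5 = 4.3; 28.8 − 23.5 = 5.3). The figure of 25 is the maximum once stage 2 opens.

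All of this stands, and it limits the size of the point. It does not answer the ordering: the planned independent check still comes after the decision, and 5.4.1 still names no governing reading.

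**Conclusion.** The point holds as a matter of timing and of an unstated rule. The harm from timing is extra accrual to an inactive cohort. Under the borrowed inflation, early termination falls from 0.54 to 0.37 or 0.33 and expected size rises from 23.5 to 27.8 or 28.8. If confirmation errors are independent, the loss is about 0.01 in early termination. These figures assume a true rate of 5% and over-reading only; the documents supply no misreading rate.

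A reader might infer that late review inflates type I error to 0.29 or 0.36. The documents do not support that. Those values need local reads to decide 4/37 as well, which the plan does not say. If the completion review decides it, type I error is 0.099 to 0.101, and late review alone cannot take it above 0.112. The gap between about 0.10 and about 0.3 is the reason to name the governing reading. This is a cheap improvement to the plan; the design's own arithmetic is correct.

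**What to change.** In 5.2 and 5.4.1, state that:

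1. the independent expert already planned reviews the scans of each confirmed, claimed stage-1 responder before stage 2 opens in that cohort;
2. only confirmed, independently reviewed PR or CR count in both the 0/12 and the 4/37 rules;
3. the local-read response rate is reported as supportive.

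The cost is protocol wording, earlier reading of a handful of scans by the same expert, and a short wait at the stage-1 decision. It adds no patients and no procedures.
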